7.1. Patient Identification and Informed Consent

COPD patients under care at, or referred to the UNC Hospitals Pulmonary Specialty Clinic, who meet the basic entry criteria will be identified by the PI or site clinical personnel. Once a patient is identified as meeting all study criteria, they will be called on the telephone by the investigator/study staff and the study will be thoroughly explained. Verbal informed consent, following UNC Guidelines for verbal consents, will be obtained after the participant has had a chance to have the consent fully explained, have all questions answered, demonstrates an understanding of the study purpose (through verbal discussion with consenter) and has agreed to participate in the study. Verbal consent to HIPAA requirements will also be documented.

7.2. Study Home Equipment

All measurement devices placed in the patient's home are FDA cleared for their intended use. These include a home spirometer (GoSpiro®, Monitored Therapeutics, Dublin, OH) and a finger pulse oximeter (3230 Pulse Oximeter, Nonin Medical, Plymouth, MN). Both of these devices are Bluetooth capable, requiring no wires for connection to the GoHome™ Personal Health Monitor data collection platform.

The GoHome is built on a Samsung tablet working with the Android operating system. It is an auto-start system requiring no patient tablet knowledge to operate the system. Its "home" page is a clock and calendar with a five-day weather forecast which is always kept on. At appropriate times, it will receive and display messages and reminders for the patient. It has a Bluetooth radio for connecting to the spirometer and pulse oximeter. The GoHome will also be used for collecting the Quality of Life questionnaires and for providing educational information for the patient.

Communication with the MTI CarePortal cloud server from the GoHome is through either Wi-Fi or its built-in cellular radio. Patients will not be able to access the internet for personal use on these devices, they will only be able to transfer data for the purposes of this study.

Eligible patients will be sent a participation kit containing the GoHome, GoSpiro and pulse oximeter following their completion of the informed consent and HIPAA authorization. A virtual (phone or video) appointment will be made with the patient by the study staff to train the patient at home how to operate the technology and confirm eligibility. Additional videos on the GoHome will provide additional instructions on use of the GoHome and GoSpiro.

7.3. Study Data Platform

Data collected from patients' homes will be stored on the MTI CarePortal (See Section 10), a cloud server hosted in Dublin, Ohio. This portal will monitor all data received or expected to be received and will send alerts via text and/or e-mail to the investigative team based on pre-defined thresholds. These alerts will be sent for missed spirometry sessions as well as for spirometry which falls below alert thresholds. It will also send alerts based on oxygen saturation alarm thresholds as well as missed medications or measurements or changes in their CAT score.

The platform will also:

- Remind patients to take their medications
- Remind patients to perform measurements
- Send patients helpful information
- Execute a UNC clinic established COPD Action Plan

7.4. Study Procedure

Patients will be enrolled in the study for up to fifteen (15) weeks, including twelve (12) weeks for active monitoring. The study timeline for all procedures is defined in the Section 17 table. All patients enrolled in the study, following the collection of a verbal informed consent, will have a medical history recorded by phone. Upon confirmation of basic eligibility, patients will be sent a telemonitoring system consisting of the GoSpiro®, a pulse oximeter and a GoHome tablet. A member of the Clinic research staff will schedule a (virtual (phone or video) appointment with the patient for when the system has arrived. They will train each patient on how to use the devices and will instruct the patient how and when to record measurements. Pulse oximetry (SpO2 and HR), as well as slow and forced spirometry with the GoSpiro will be collected during this training call. These instructions will also be provided on patient information material (See Appendices A and B). Patients should exhibit proficiency with the devices and demonstrate understanding of the measurement schedule prior to ending the call.

The study nurse will contact the patient the following day by phone to confirm that the patient is able to set up the GoHome and use the devices for measurements. In the event the participant is not able to provide and transmit satisfactory data collection after one week (due to technical or training reasons) they will be removed from study and replaced with another participant toward the total recruitment goal. The study nurse will call the patient every four (4) weeks to collect information on any changes to inhaled medication, steroids or antibiotics and assist the patient with any operational questions. Between phone calls, Clinic research staff or device manufacturer's support personnel will be available to assist the patient should questions or technical issues arise. The study nurse will conduct a final phone visit to collect close out data prior to the participant returning the devices (see Section 17).

Physiologic data from the patients will be transmitted automatically following each measurement and will be available on the CarePortal within a few minutes of its collection. Physiologic data (spirometry and oxygen saturation) will be collected every day. Medication reminders, COPD Action Plan communications, etc. will be sent every day if scheduled. In addition to monitoring parameters, health

teaching tips as part of the COPD Action Plan will also be incorporated into the GoHome software to educate and motivate patients regarding self-care. A Quality of Life questionnaire (COPD Assessment Test) will also be collected every 4 weeks from the patients through the GoHome tablet.

At the end of study (after completion of final phone visit), the patients will return the equipment to UNC via a pre-paid FedEx air bill that has been included with the original shipment. A member of the Clinic research study team will have a final call with the patient to check on the patient's respiratory status and have them complete a usability questionnaire by phone.

8. Quality Control Measures

Quality control of the lung function measurements will include automatic ATS/ERS intra-measurement grading of the forced flow-volume loops and slow spirometry to ensure interpretable and actionable home spirometry.⁵ MTI will assist with determining the number of missed spirometry sessions with seven times per week testing, and determining any technical issues in transmission of data from the spirometer to the MTI CarePortal.

The GoSpiro home spirometer meets the 2019 ATS/ERS criteria for accuracy and reproducibility.⁵ Baseline pulmonary function will be defined as the mean FEV1 over the first two weeks of the study (six measurements). If older data is available for the patient, that data may be included in establishing historic values for analysis. Variability of pulmonary function for alerts to Clinic staff will include a decrease by one personalized z-score using pulmonary function measurements for an individual patient and calculated over the length of the study as well as using historic data if available.

Alerts from acute declines in pulmonary function will be defined as any decrement in either FEV1, FVC or IC >10%. Oxygen saturation readings below 88% will trigger an alert. For patients being managed with DPI delivered inhaled drugs, monitoring of peak inspiratory flow for detection of inadequate flows to aerosolize and deliver the powder, will also generate alerts. The MTI CarePortal will provide daily reports to the Clinic research staff of patient trending towards alert levels, as well as patients with low adherence to medications or measurements.

9. Assessments

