9.2.10. Usability Questionnaire

At the End-of-Study phone call, the patient will be given a brief Usability Questionnaire to collect their opinions on use of the GoSpiro and GoHome, both for usability and perceived value to them and the management of their health. The Usability Questionnaire is in the Appendices.

10. Data Collection and Confidentiality Procedures

The data collection tablets placed in patients' homes are based on the Android operating system. They are locked down with a Samsung Knox Mobile Device Management (MDM) control system that prevents anyone from making changes to the programs or applications. Although the tablets connect with the MTI CarePortal via the internet (either Wi-Fi or cellular), patients have no access to the internet outside of the applications running on the tablet.

For each patient, a randomized numeric token is sent to the data collection device in their home. All data collected from proprietary data collection devices such as the GoHome Personal Health Monitor or the GoClinic Android tablet are then returned to the server with the token. When received, the server reidentifies the data based on the token number and locates the data in the appropriate patient file. No personal health information (PHI) is ever transferred between a remote location and the MTI CarePortal. The access to the data storage system on the MTI CarePortal is limited to web browsers (SSL Secured), direct messaging and electronic data transfer facilitated with a data token.

The MTI CarePortal cloud server, where the data is stored, is hosted by Expedient Inc. with the main server located in, Dublin, OH. Operating mirrored drives, data is backed up in Pittsburgh, PA. The system contains a disaster recovery center in Carmel, IN. Expedient is a global data management company that complies with HIPAA, HITRUST and GDPR requirements for data security.

Settable authorization levels limit users to a) inquiry (read only) capabilities, b) inquiry with also the ability to set alarm limits, establish reminders, care plans and the like, and c) full access for editing and updating capabilities depending on the level of authorization. Users have no access to the underlying code running the user facing application or the MTI CarePortal infrastructure.

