Differences between important continuous variables at two specific times will be evaluated with the two-sided paired t-test ($P<0.05$). Important categorical events such as changes in FEV1, Inspiratory Capacity, QoL, medication adherence, rehospitalization and incidence of adverse events will be evaluated by constructing 95% confidence limits in their incidence, and also with descriptive statistics. In addition, the results will be used to identify technological deficiencies and provide data to inform the power requirements for future studies.

Primary Endpoint Definitions

The first primary endpoint variable for this study is the change from baseline in Total Score of COPD Assessment Test (CAT). The total CAT score is calculated by summing the scores of all items and ranges from 0 to 40, higher scores indicating severe condition. The change will be calculated as the CAT score at Week 12 minus the CAT score at Enrollment. A negative change in CAT score will indicate an improvement in patient status.

The second primary endpoint variable for this study is adherence to performing scheduled measurements and responding to scheduled questionnaires. For each subject the adherence will be recorded based on the data uploaded to the CarePortal. The adherence percentage will be calculated by the difference in recorded measurements and answered questionnaires versus the scheduled measurements and questionnaires.

Analysis of Primary Endpoints

The primary outcomes will be reported as proportions with 95% confidence intervals, on the FAS.

Secondary Endpoint Definitions

The prespecified secondary endpoints for this study will include:

- Participant satisfaction survey scores at 3 months (Time frame: 3 months) defined as the percentage of participants with score of 4 or higher on individual survey domains. A satisfaction survey (investigator-developed, 15 questions, each question is graded on a scale of 1-5, 1 being not at all and 5 being extremely) will be used to measure home spirometry and table ease and usefulness.
- Rate of self-reported COPD exacerbations (Time frame: 3 months) defined as the 30-day COPD exacerbation rate, defined as the mean number of events/30 days of follow-up (using three months of follow-up data). COPD exacerbation events are defined as self-reported COPD exacerbations requiring treatment with antibiotics or steroids.

Analysis of Secondary Endpoints

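### The satisfaction endpoint is very likely collected by phone by the clinic research team that trained and supported the patient, which risks a modest upward shift that self-completion could largely avoid

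*Combined protocol and SAP*

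**What the plan says.** Section 7.4 describes the close-out contact: "A member of the Clinic research study team will have a final call with the patient", to ask about respiratory status and to "have them complete a usability questionnaire by phone". Section 9.2.10 agrees: "At the End-of-Study phone call, the patient will be given a brief Usability Questionnaire to collect their opinions on use of the GoSpiro and GoHome". The schedule in Section 17 shows the usability survey once, at the week 13 final call.

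Section 7.4 also says who delivers the programme. Of the clinic research staff it says "They will train each patient on how to use the devices and will instruct the patient how and when to record measurements". The study nurse phones the next day and every four weeks, partly to "assist the patient with any operational questions". Between those calls, "Clinic research staff or device manufacturer's support personnel will be available to assist the patient should questions or technical issues arise".

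In Section 13 (Secondary Endpoint Definitions) participant satisfaction at 3 months is "defined as the percentage of participants with score of 4 or higher on individual survey domains", from an investigator-developed survey of 15 questions scored 1 to 5. It is reported as a proportion with a 95% confidence interval. Section 13 does not say how the survey is administered.

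A self-completion route exists for the other questionnaire. Section 7.2 says: "The GoHome will also be used for collecting the Quality of Life questionnaires and for providing educational information for the patient".

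**The concern.** Patients are asked how easy and useful the system is by the team that introduced it, taught it and helped with it, and that belongs to the clinic managing their COPD. The same call reviews their breathing. A patient who would privately give a 3 has some reason to say 4. The plan provides no self-completed form, no interviewer from outside the team and no caveat in the analysis.

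Acceptability to patients is a stated purpose of the study (Section 4.2), and Section 13 sets out to determine acceptance and value. This survey asks for the patient's opinion directly. A shift here would act in one direction, in a single-arm study where no other group shares and cancels it.

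**Working it through.** The plan states no target or expected value for the satisfaction share, so there is no figure to reproduce. The check has two parts.

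**1. Does the text support the mechanism?**

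- *Is it one instrument?* Sections 7.4 and 9.2.10 speak of a usability questionnaire, and Section 13 of a satisfaction survey. They are never expressly equated. Section 17 schedules only one such survey, the appendix list holds only one (Appendix D), and both descriptions concern the home devices and their usefulness. One instrument is very likely.
- *Is it the same team?* Yes. Section 7.4 assigns training, support and the final call to clinic research staff. It does not say that one person does all three.
- *Is another route feasible?* Yes. The CAT is collected on the tablet. Section 9.2.9 describes tablet messages in multiple-choice or slide-bar format with stored answers. Section 7.4 puts the final phone visit before the devices are returned, in a pre-paid shipment.

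**2. How large could the shift be?**

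Inputs: n = 12 (synopsis; Section 6) and the cut at 4 or higher (Section 13). The courtesy rate c is the share of participants truly below 4 who report 4 or 5. The documents do not give it, so 10% to 50% is assumed. The upward direction is also an assumption, drawn from the setting.

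One changed answer moves the share by 1/12 = 8.3 points. From 7/12 = 58%, one change gives 8/12 = 67% and three give 10/12 = 83%.

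Reported share = p + (1 − p) × c, where p is the true share. For p = 60% and c = 20%: 0.60 + 0.40 × 0.20 = 0.68.

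| True share p | c = 10% | c = 20% | c = 30% | c = 50% |
|---|---|---|---|---|
| 50% | 55% | 60% | 65% | 75% |
| 60% | 64% | 68% | 72% | 80% |
| 70% | 73% | 76% | 79% | 85% |

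For a true share of 60%, the binomial chance of seeing 9 or more of 12 is 22.5% without a shift, 43.2% at c = 20% and 55.5% at c = 30%.

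Exact (Clopper-Pearson) 95% intervals at n = 12:

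| Observed | Share | 95% interval |
|---|---|---|
| 8/12 | 67% | 35% to 90% |
| 9/12 | 75% | 43% to 95% |
| 10/12 | 83% | 52% to 98% |

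These intervals describe sampling error alone. A shift moves the whole interval upward without widening it to allow for the bias.

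**The case against.** The strongest reply is that little depends on this endpoint. It is secondary and descriptive, with no threshold or go/no-go rule. The sample is declared unpowered, and an interval of 35% to 90% for 8/12 supports no firm decision whatever the mode. Sections 1 and 13 name adherence and use of the platform as the guide for future trials. Adherence is computed from uploaded data, so the interview cannot affect it. All of this stands, and it limits the weight of the point. It does not justify leaving in place a one-directional error that is cheap to reduce.

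The mechanism also has limits. The survey rates the devices, and nothing cited asks patients to rate staff, so the courtesy motive is indirect. A reader might infer that staff read the items aloud, or that the trainer conducts the interview. The documents say only that the questionnaire is completed by phone with a team member, and Appendix D is listed by title, so its instructions cannot be checked.

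Self-completion has a bias of its own. A tablet-only survey could lose the people who find the tablet hard, who may be the low scorers. A form carrying a subject number remains linkable by the study team. Phone fallback would fall mainly on the less engaged, so mode would be mixed up with engagement. These objections stand. They favour paper over tablet, and they rule out a comparison by mode.

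Collecting close-out data by phone is a coherent choice after version 2.0 removed in-person visits. Self-completion is equally remote.

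**Conclusion.** The point holds as a risk of upward bias, of unknown size, in a secondary endpoint. It rests on three assumptions: that the usability questionnaire is the satisfaction survey of Section 13, that completing it by phone means giving answers to the caller, and that any courtesy effect runs upward. Under assumed courtesy rates of 20% to 30%, a true 60% would be reported as 68% to 72%. These figures show sensitivity and are not estimates.

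A reader might infer that the satisfaction result will be invalid, or that it would by itself carry a decision to run a larger trial. The documents support neither: they contain no evidence on the size of the effect, attach no decision rule to this endpoint, and look to adherence and use for guidance. The impact is modest, and the change is worth making because it costs little.

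**What to change.** 1. State in Sections 7.4, 9.2.10 and 13 whether the usability questionnaire and the satisfaction survey are the same instrument, and how it is administered.
2. Have participants complete it themselves shortly before the final call and before the equipment goes back. A paper form sent with the kit and returned in the same shipment is preferable, so that those who struggle with the tablet are not lost. The GoHome tablet is the alternative.
3. Use the phone only for forms not completed.
4. Record the mode for each participant. Report the pooled proportion with its 95% confidence interval and the number collected by each mode. Make no subgroup comparison by mode, which would be uninformative with 12 participants.
5. State as a limitation that answers are linkable through the subject number, and that any phone answers were given to the study team.

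The cost is one sheet in the kit or one form on the tablet, slightly more follow-up of non-response, and a possible mix of modes. Clinical management does not change.

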Exploratory Endpoints	
 Thirty (30) day exacerbation stratified by FEV1 Adherence to subcomponent measurements Quality of home forced spirometry measures Variability in slow spirometry and correlation of change in slow spirometry values with COPD exacerbation Quality of life scores at each visit Total number of clinical interventions by type (what the medical staff does in response to the telemonitoring) Peak inspiratory flow measurements Adherence to taking prescribed medications
Patient Selection Criteria	
Inclusion Criteria:
 
 Male or Female patients 40 to 80 years of age English speaking Spirometry confirmed COPD (post-BD FEV1/FVC<0.70) and post-BD FEV1% predicted <80% at screening visit. (Target 50% of recruitment with post-BD FEV1<50% predicted (severe obstruction). Spirometry must have been collected within 24 months prior to screening. Increased COPD exacerbation risk defined as either of the following in the prior 12 months: 
 One hospitalization for COPD exacerbation Two outpatient COPD exacerbations requiring treatment with steroids and/or antibiotics Signed informed consent 
Exclusion Criteria:
 
 Unable to perform spirometry on their own following training. Planned discharge to a nursing home or other extended care facility Co-morbid conditions likely to result in non-preventable

	
readmissions (e.g., terminal malignancy, cirrhosis or end-stage liver disease, chronic wound infections, etc.)
 
 • Uncontrolled or untreated medical conditions that would predispose the patient to recurrent COPD exacerbations (i.e., bronchiectasis) • Patient refusal to or inability to comply with monitoring requirements, for any reason including but not limited to dementia, a history of dementia, or other significant mental impairment • Patients enrolled in any other clinical trials or therapeutic studies of drugs, devices, or biologics
Safety Monitoring	As this study is deemed low risk, oversight for this feasibility study will be conducted by the PI ([name]). The PI will monitor data to ensure the safety of participants.

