9.2.3. Spirometry

Patients will be performing slow spirometry measurements five (5) times per week on Sundays, Mondays, Wednesdays, Fridays and Saturdays. They will be performing forced spirometry measurements on Tuesdays and Thursdays. Measurements will be performed in the morning at least 15 minutes following them taking their inhaled medications. The reliability and repeatability of effort dependent tests or tests that require patients to follow specific steps, depend on patients understanding how to perform the test.

The GoHome comes with Avatar-Assisted-Technology to coach the patient through each measurement. The Avatar follows ATS/ERS recommendations for instructions and coaching. At the end of each measurement, the Avatar reviews the results and instructs the patient how to correct maneuver errors. All of this takes place without human intervention. Experience to date indicates that use of the Avatar-Assisted-Technology results in data collection as good as from hospital PFT laboratories and better than from physician offices.³

Spirometry will be performed in accordance with the 2019 ATS/ERS recommendations for intra-measurement performance. To increase adherence to performing spirometry measurements, a Statistical Process Control approach will be used as recommended for COPD patients.⁴ This approach will be used for both FVC and SVC testing.

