The secondary endpoints will be reported as proportion with 95% confidence interval of participants with score of 4 or higher on individual survey domains of patient satisfaction summary score; Descriptive analysis of patient satisfaction summary scores will include mean (SD), median (IQR), range of scores.

For the COPD exacerbation analyses, the proportion of patients with COPD exacerbations and the rate of exacerbations occurring during follow-up will be reported along with 95% CI. A patient will be considered censored for exacerbations at the time of the last documented visit, the end of the study, or death (whichever occurs earlier), if they did not experience an exacerbation before.

Exploratory Endpoints Definitions

The study contains exploratory endpoints to examine individual components of the monitoring functions and their impact. These include:

- Rate of self-reported COPD exacerbations stratified by FEV1 and defined as the 30-day COPD exacerbation rate, defined as the mean number of self-reported COPD exacerbations

requiring treatment with antibiotics or steroids per 30 days of follow-up (averaged using 3 months of follow-up data), stratified by FEV1 (separately <50% predicted and >=50% predicted).

- Home spirometry measurement collection adherence defined as the percentage of participants achieving >50% completion of spirometry measurements over three months.
- Home pulse oximetry measurement collection adherence defined as the percentage of participants achieving >50% completion of pulse oximetry over three months.
- Home questionnaire collection adherence defined as the percentage of participants achieving >50% completion of home questionnaires over three months.
- Quality of home forced spirometry measures defined as the percentage of forced home spirometry measurements that meet ATS quality standards
- Change from baseline on COPD Assessment Test (CAT) Total Score defined as the CAT scores measured at baseline, week 4, week 8 and week 12 and the median (SD) change in CAT score from baseline will be calculated at each time point.
- Inspiratory Capacity variability defined as the coefficient of variation will be calculated by dividing standard deviation of Inspiratory Capacity values by the mean of the inspiratory capacity values. Inspiratory capacity measured via slow vital capacity maneuver will be performed at home five days per week during duration of study.

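### The spirometry quality endpoint covers forced tests only, leaving 60 of each participant's 84 scheduled sessions, the slow ones, with no prespecified quality summary

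*Combined protocol and SAP*

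**What the plan says.** Section 8 (Quality Control Measures) applies "automatic ATS/ERS intra-measurement grading of the forced flow-volume loops and slow spirometry to ensure interpretable and actionable home spirometry". Grading is therefore planned for both kinds of manoeuvre.

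The synopsis lists one spirometry quality outcome among its exploratory endpoints: "Quality of home forced spirometry measures". Section 13 defines it as "the percentage of forced home spirometry measurements that meet ATS quality standards" and analyses it as a proportion with a 95% confidence interval. Neither place gives a counterpart for slow spirometry.

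The timetable is in Section 9.2.3: "Patients will be performing slow spirometry measurements five (5) times per week on Sundays, Mondays, Wednesdays, Fridays and Saturdays", and "They will be performing forced spirometry measurements on Tuesdays and Thursdays". The synopsis, Section 4.2 and the footnotes to the Section 17 schedule give the same days.

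Section 13 states that inspiratory capacity comes from the slow manoeuvre. It plans two analyses of it: the coefficient of variation, and a comparison of the weeks around each exacerbation. Section 8 also makes a fall of more than 10% in inspiratory capacity one of the triggers for an alert to staff.

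**The concern.** The study describes itself as a technical evaluation whose results should expose weaknesses in the technology and inform later trials. Whether patients at home, coached only by the tablet, produce usable manoeuvres is one of its main practical questions. The endpoint that answers it is limited to the less frequent type of test.

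Nothing else in the analysis plan fills the gap:

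- **Adherence** is counted from what reaches the CarePortal, and its definition carries no quality condition. A poor slow manoeuvre that uploads counts as done.
- **The inspiratory capacity coefficient of variation** mixes inconsistent technique with real change in the patient. A high value cannot be interpreted without knowing how many manoeuvres were acceptable.
- **The general aim of identifying technological deficiencies** does not mention slow-test quality.

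At stake is whether the trial can say that slow spirometry at home is good enough to support an alert or a future endpoint. If slow-test grades are examined only after the fact, whether and how they are reported becomes a choice made with the data in view.

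**Working it through.** **Inputs**

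- Slow sessions per week: 5 (Section 9.2.3).
- Forced sessions per week: 2 (Section 9.2.3).
- Monitoring period: Section 7.4, "including twelve (12) weeks for active monitoring".
- Planned participants: 12 (synopsis and Section 6).

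**Check against the plan's own figure.** Section 8 speaks of counting missed sessions "with seven times per week testing". 5 + 2 = 7, so the weekly total is reproduced. The documents do not themselves state 60 or 84; these follow from the timetable.

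**Scheduled sessions**

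| | Per week | Per participant (× 12 weeks) | All participants (× 12) | Share |
|---|---|---|---|---|
| Slow | 5 | 60 | 720 | 60/84 = 71.4% |
| Forced | 2 | 24 | 288 | 24/84 = 28.6% |
| Total | 7 | 84 | 1,008 | 100% |

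**Does the majority depend on how the schedule is read?**

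- Three months taken as 13 weeks: 5 × 13 = 65 slow of 7 × 13 = 91, which is 71.4%.
- One slow and one forced test added from the training call: (60 + 1)/(84 + 2) = 61/86 = 70.9%.
- Section 8 bases baseline FEV1 on six measurements in two weeks, whereas the Tuesday and Thursday timetable gives 2 × 2 = 4. If six meant three forced sessions a week within seven, slow sessions would be 4 × 12 = 48 of 84, or 57.1%.

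Slow spirometry is the majority under every reading. The six-against-four mismatch is a separate matter that the sponsor needs to reconcile; it does not change this point.

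**Where each quality statement applies**

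| | Forced | Slow |
|---|---|---|
| Automatic grading (Section 8) | yes | yes |
| Quality endpoint (synopsis) | yes | no |
| Quality endpoint definition (Section 13) | yes | no |
| Quality endpoint analysis (Section 13) | yes | no |

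The two pass rates need not be close, because the manoeuvres differ. The documents give no pass rate for either, so no figure for slow-test quality can be derived from them.

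**The case against.** The strongest reply is that the plan contains no contradiction. The endpoint is called forced in the synopsis, the definition and the analysis alike. Section 8 describes a quality-control procedure and does not promise an endpoint for everything it grades. The study is an unpowered evaluation in 12 patients, and this is one of many exploratory outcomes. Forced tests also carry much of the information: FEV1, FVC and peak inspiratory flow, each tied to an alert. All of that stands, and it limits the point to the scope of one exploratory endpoint.

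It is also fair that slow-test performance is not neglected during the trial. The avatar reviews each measurement and corrects errors, a process-control approach is used for both manoeuvres, and participants who cannot deliver satisfactory data after a week are replaced. These measures may raise quality, but none of them reports it.

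Three stronger readings are tempting, and the documents do not support them:

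- **That 71.4% of sessions have no quality assessment.** Section 8 says slow tests are graded; what is missing is a prespecified summary. The percentage also refers to scheduled sessions, not completed ones.
- **That the forced result would mislead.** It is labelled as forced, and it is correct for what it names. A reader might generalise from it, but that would be the reader's inference.
- **That slow-test quality is poor, or that the trial could never show it.** No document gives a pass rate, and the summary could still be added if the grades can be retrieved.

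One further objection bears on the remedy. The documents say that grading happens, but not that each grade is stored or can be exported. They also do not say which grade counts as a pass for a slow manoeuvre. Both need an answer before the percentage can be calculated.

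**Conclusion.** The point holds as a gap in the scope of an exploratory endpoint. The plan grades both manoeuvres but prespecifies a quality summary only for the type that makes up 24 of 84 scheduled sessions. The other 60 (71.4%) feed two inspiratory capacity endpoints and one alert, and the trial as planned would not report whether they are of usable quality. Section 5.2 lists slow-spirometry variability and its relation to exacerbation as secondary, while the synopsis and Section 13 treat them as exploratory. Under either label, their interpretation depends on manoeuvre quality.

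Neither primary endpoint, adherence or CAT, is affected. The conclusion rests on the stated timetable and on Section 8 meaning what it says about grading slow tests. It needs no assumption about actual pass rates.

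**What to change.** Extend the quality endpoint in the synopsis and in Section 13 (definition and analysis) as follows:

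1. Report, separately for forced and slow spirometry, the percentage of uploaded home measurements that meet the automatic grading of Section 8.
2. State which grade counts as a pass for each manoeuvre. Section 13 now refers only to ATS standards for forced tests and gives nothing for slow tests.
3. Calculate the percentage within each participant, then summarise across participants by median, IQR and range. Repeated measurements from one person are not independent. A simple binomial interval on up to 288 forced or 720 slow measurements would treat data from 12 people as that many separate observations.
4. Leave out the manoeuvres from the training call. They are done with staff support and do not represent unsupervised use.
5. Confirm that slow-test grades are kept and can be exported from the CarePortal.

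If the grades can be exported, the cost is SAP wording and one more table. No new tests or visits are needed, and patient care does not change.
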